18.2 DERIVED VARIABLES

Not applicable.

18.3 REPEATED OR UNSCHEDULED ASSESSMENTS OF SAFETY PARAMETERS

Baseline is defined as the last assessment made before the first dose of lead-in study treatment. If end-of-study assessments are repeated or if unscheduled visits occur, the last nonmissing postbaseline assessment will be used as the end-of-study assessment for generating summary statistics. However, all postbaseline assessments will be used for PCS value determinations, and all assessments will be presented in the data listings.

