4.0 INTRODUCTION

This statistical analysis plan (SAP) provides a more technical and detailed elaboration of the statistical analyses of the safety data as outlined and/or specified in the final protocol of Study 3101-309-002 (dated 22 Feb 2019) and protocol amendment 1 (dated 15 Sept 2020). Specifications of tables, figures, and data listings are contained in a separate document.

Study 3101-309-002 is a Phase 3, multicenter, open-label, 40-week, long-term safety extension study conducted in the United States and will enroll approximately 750 participants from the United States. Participants will be treated with atogepant 60 mg once daily.

The study will consist of a 40-week open-label treatment period, and a safety follow-up period of 4 weeks.

Participants will directly rollover from Study 3101-301-002 (Phase 3 EM). As such, participants will have Visit 7 from Study 3101-301-002 function as the Visit 1 for this study after the participant signs the informed consent. After Visit 1, study visits will occur every 4 weeks for the duration of the study. An EOS Visit will occur 4 weeks after the last dose of atogepant.

Note, there may be participants who complete Visit 7 in the lead-in Study 3101-301-002 before extension Study 3101-309-002 has been initiated. Those participants should complete Visit 7/ET and Visit 8/EOS Visit (including discontinuation of study intervention) per the Study 3101-301-002 Schedule of Visits and Procedures.

[figure not shown]
Depending on the timing of the initiation of this extension study, in relation to each participant's planned Visit 8 schedule, Visit 1 Study 3101-309-002 can be conducted on the same day as Visit 8/EOS Visit for Study 3101-301-002 or soon thereafter.

- If this extension study is initiated prior to the participant's planned Visit 8 in the lead-in study, then Visit 8/EOS Visit for Study 3101-301-002 should be conducted on the same day as Visit 1 for Study 3101-309-002.
- If this extension study is not initiated prior to the participant's planned Visit 8 in the lead-in study (ie, there is a gap between Visit 8 and Visit 1), then Visit 8/EOS Visit should be conducted as planned per the Study 3101-301-002 Schedule of Visits and Procedures. When this extension study is initiated, the participant should return to the clinic as soon as possible, and Visit 1 should be conducted per the Study 3101-309-002 Schedule of Visits and Procedures.

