7.0 PARTICIPANT DISPOSITION

Screen-failures and the associated reasons for failure will be tabulated for all screened participants.

The number of participants in the 2 study populations (Screened, Safety) will be summarized overall.

The number of participants in the safety population will be summarized by lead-in study treatments (placebo, Atogepant 10 mg, Atogepant 30 mg, Atogepant 60 mg) and enrollment category (3101-301-002 Visit 7 Completer, 3101-301-002 Visit 8 Completer, 3101-301-002 Study Completer) and overall.

The number and percentage of participants who enter the open-label treatment period, complete the open-label treatment period and of participants who prematurely discontinue during the same period will be presented for the Safety Population. The reasons for premature discontinuation from the open-label treatment period will be summarized (number and percentage). Similar disposition information to the treatment period will be presented for the safety follow-up period. All participants who prematurely discontinue during the open-label treatment period or the safety follow-up period will be listed by discontinuation reason.

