11.2 CLINICAL LABORATORY PARAMETERS

Descriptive statistics for clinical laboratory values (in SI units) at baseline, postbaseline, and changes from baseline values at each postbaseline timepoint will be presented for the following laboratory parameters.

In addition, descriptive statistics for values and changes from the baseline values in conventional units at each assessment time point will be presented for selected clinical laboratory parameters listed in [Appendix I](#). A description of reporting the lab values in conventional units in patient narratives (along with the standard reporting in SI units) is presented at the end of [Appendix I](#).

Hematology: Hemoglobin, hematocrit, red blood cell count, red blood cell indices (mean corpuscular volume, mean corpuscular hemoglobin, mean corpuscular hemoglobin concentration), white blood cell count, including differential (neutrophils, lymphocytes, monocytes, eosinophils, and basophils), platelet count

Chemistry: Sodium, potassium, chloride, bicarbonate, glucose, blood urea nitrogen, creatinine, total bilirubin, alkaline phosphatase, aspartate aminotransferase, alanine aminotransferase, lactate dehydrogenase, creatine kinase, total protein, albumin, calcium, phosphorus, uric acid, total cholesterol, estimated glomerular filtration rate

Urinalysis: Specific gravity, pH

Clinical laboratory test values will be considered potentially clinically significant (PCS) if they meet either the lower-limit or higher-limit PCS criteria listed in [Table 11-1](#). The number and percentage of participants who have PCS postbaseline clinical laboratory values will be tabulated. The percentages will be calculated relative to the number of participants with available non-PCS baseline values and at least 1 postbaseline assessment. The numerator will be the total number of participants with available non-PCS baseline values and at least 1 PCS postbaseline value during the study. A supportive tabular display of participants with PCS postbaseline values will be provided, including the participant identification (PID) number, baseline and all postbaseline (including non-PCS) values.

In addition, a tabular display showing all AEs that occurred in participants who had PCS postbaseline clinical laboratory values will be provided.

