The number and percentage of participants meeting each of the following criteria for postbaseline hepatic laboratory abnormalities listed in Table 11-2 will be summarized. The percentages will be calculated relative to the number of participants with at least 1 available postbaseline assessment. The numerator will be the total number of participants having at least 1 postbaseline value that meets the specific category during the study. A supportive listing will also be provided.

Table 11-2 Criteria for Hepatic Laboratory Abnormalities

Laboratory Parameter	Categories
ALT	$\geq 1 \times \text{ULN}$
	$\geq 1.5 \times \text{ULN}$
	$\geq 2 \times \text{ULN}$
	$\geq 3 \times \text{ULN}$
	$\geq 5 \times \text{ULN}$
	$\geq 10 \times \text{ULN}$
	$\geq 20 \times \text{ULN}$
AST	$\geq 1 \times \text{ULN}$
	$\geq 1.5 \times \text{ULN}$
	$\geq 2 \times \text{ULN}$
	$\geq 3 \times \text{ULN}$
	$\geq 5 \times \text{ULN}$
	$\geq 10 \times \text{ULN}$
	$\geq 20 \times \text{ULN}$
ALT or AST	$\geq 1 \times \text{ULN}$
	$\geq 1.5 \times \text{ULN}$
	$\geq 2 \times \text{ULN}$
	$\geq 3 \times \text{ULN}$
	$\geq 5 \times \text{ULN}$
	$\geq 10 \times \text{ULN}$
	$\geq 20 \times \text{ULN}$
Bilirubin Total	$\geq 1 \times \text{ULN}$
	$\geq 1.5 \times \text{ULN}$
	$\geq 2 \times \text{ULN}$
	$\geq 3 \times \text{ULN}$
	$\geq 5 \times \text{ULN}$
	$\geq 10 \times \text{ULN}$
	$\geq 20 \times \text{ULN}$
Alkaline Phosphatase	$\geq 1 \times \text{ULN}$
	$\geq 1.5 \times \text{ULN}$
	$\geq 2 \times \text{ULN}$
	$\geq 3 \times \text{ULN}$
	$\geq 5 \times \text{ULN}$
	$\geq 10 \times \text{ULN}$
	$\geq 20 \times \text{ULN}$

Laboratory Parameter	Categories
Concurrent Elevations ¹	ALT or AST $\geq 3 \times$ ULN and Bilirubin Total $\geq 1.5 \times$ ULN ALT or AST $\geq 3 \times$ ULN and Bilirubin Total $\geq 2 \times$ ULN
Potential Hy's Law within 24-hour window ¹	Postbaseline assessment of the following laboratory parameters based on blood draws collected within a 24-hour period: 
• ALT or AST $\geq 3 \times$ ULN• TBL $\geq 2 \times$ ULN• ALP $< 2 \times$ ULN
e-DISH	Postbaseline assessment of the following laboratory parameters at any time: 
• Maximum ALT or AST $\geq 3 \times$ ULN• Maximum TBL $\geq 2 \times$ ULN

ALT = alanine aminotransferase; AST = aspartate aminotransferase; TBL = total bilirubin;
ALP = alkaline phosphatase; ULN = upper limit of normal (value provided by the laboratory).

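### The SAP gives postbaseline no open-label start for most lab, vital-sign and ECG counts, so pre-dose Visit 1 values of gap entrants count as open-label findings

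*SAP*

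**What the plan says.** SAP 18.3 fixes the reference point: "Baseline is defined as the last assessment made before the first dose of lead-in study treatment". It adds that "all postbaseline assessments will be used for PCS value determinations". The SAP does not define postbaseline any further.

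The counting rules in 11.2 to 11.4 use that term. The lab PCS numerator takes participants with "available non-PCS baseline values and at least 1 PCS postbaseline value during the study". Table 11-2, the hepatic categories, counts "participants having at least 1 postbaseline value that meets the specific category during the study". The vital-sign and ECG PCS numerators use the same time limit. The table of QTcF increases above 30 and above 60 msec states no period.

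Participants reach Visit 1 by three routes, which SAP 7.0 lists as "3101-301-002 Visit 7 Completer, 3101-301-002 Visit 8 Completer, 3101-301-002 Study Completer". SAP 4.0 says of direct rollovers that "participants will have Visit 7 from Study 3101-301-002 function as the Visit 1 for this study". Of those who return after a gap it says that "Visit 1 should be conducted per the Study 3101-309-002 Schedule of Visits and Procedures". Protocol 8.4.1.1 lists the Visit 1 labs, vital signs and ECG ahead of dispensing.

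Two other parts of the SAP do have an open-label start. Section 11.1 summarizes only TEAEs that begin on or after the first open-label dose date. The End of Study row of Table 18.1-1 is limited to assessments after treatment start.

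**The concern.** The study has one arm, one objective (safety and tolerability) and no efficacy analysis, so these counts are its result. A Visit 1 value taken before the first open-label dose reflects something other than open-label 60 mg treatment. It reflects the lead-in arm ("placebo, Atogepant 10 mg, Atogepant 30 mg, Atogepant 60 mg") or time off drug. If it is counted as postbaseline, a finding on placebo or a lower dose can appear as a 60 mg finding.

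Denominators are exposed too. They require at least one postbaseline assessment, and a Visit 1 sample meets that for someone with no on-treatment sample.

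The SAP's change log (entry for 11.1, 17 October 2019) records a sentence added for AEs captured at visits shared by the two studies. The shared-visit problem was therefore handled for AEs but not for labs, vital signs and ECGs.

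**Working it through.** The plan gives no figure to reproduce, so the check sets its start rules side by side and follows Visit 1 through them.

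**Step 1. Start rules in the SAP.**

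| Summary | Start stated | Pre-dose Visit 1 value admitted? |
|---|---|---|
| TEAEs (11.1) | First open-label dose date | Not affected |
| End of Study (Table 18.1-1) | After treatment start | No |
| Potential Hy's law (11.2) | First dose of study treatment, not said to be open-label | Unclear |
| QTcF above 450, 480 or 500 msec (11.4) | Labelled post-treatment | Unclear |
| End of Treatment (18.1) | Within the open-label treatment period | Only if no later on-treatment value exists |
| Lab PCS, rest of Table 11-2, vital-sign PCS, ECG PCS | In the study | Depends on route (Step 2) |
| QTcF increase (11.4) | None | Depends on route (Step 2) |
| Week 4 by-visit row (Table 18.1-1) | Treatment Day 1 | Yes, if the first dose is on the Visit 1 date |

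End of Treatment depends on where Visit 1 belongs. Protocol Table 1 and 8.4.1.1 place it under the open-label treatment period.

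**Step 2. By route of entry.**
- *After a gap:* Visit 1 runs under this study's own schedule. Its values are in the study, after the lead-in baseline and before the open-label dose. They meet the wording and are counted.
- *Direct rollover:* lead-in Visit 7 serves as Visit 1, which brings the values in. Footnote a of protocol Table 1 says Visit 7 procedures are not repeated, so they can also be read as lead-in data and left out.
- *Same day as lead-in Visit 8:* the no-repeat footnote names only Visit 7, so the plan does not say how these values are classed.

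**Step 3. Week 4 window.** Day 1 is the date, not the time, of first dose. If that is the Visit 1 date, Visit 1 is Treatment Day 1 and falls in the window of Days 1 to 42. Protocol Amendment 1, Section 8.5, does not fix the first-dose day. The 22 February 2019 protocol required the first dose at the site at Visit 1.
- Visit 2: 28 ± 3 = Day 25 to 31, inside the window.
- If Visit 2 is remote, its labs and vital signs move to the next in-person visit. The earliest scheduled one is Visit 3: 56 − 3 = Day 53, after Day 42. Visit 1 is then the only scheduled Week 4 lab and vital-sign record.

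**Step 4. How far Visit 1 screening protects the counts.**
- Table 11-1: 20 chemistry + 10 hematology + 4 urinalysis = 34 parameters. Protocol 8.9 sets a numeric Visit 1 limit for 4 (ALT, AST, total bilirubin, low albumin): 4/34 = 11.8%, leaving 30.
- Table 11-3: 4 measures × 2 directions + 3 orthostatic = 11 criteria. Protocol 4.3 sets a numeric limit for 2 (high systolic and diastolic pressure, sitting only), leaving 9.
- The rest rely on investigator judgement.
- QTcF limits at Visit 1 (450 msec males, 470 msec females) are absolute. With assumed values, a change from 400 to 438 msec passes both, yet 438 − 400 = 38 msec counts as an increase above 30.
- Where a limit exists, the gap to the PCS threshold is often wide: ALT and AST 1 against 3 × ULN, systolic pressure 160 against 180 mm Hg, QTcF 450 or 470 against 500 msec.

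**Step 5. Share of occasions through Week 40.** ECGs are at Visits 1, 4, 7 and 11: 1/4 = 25% at Visit 1. Labs and vital signs are at Visits 1 to 11: 1/11 = 9.1%. These are shares of scheduled occasions, not of flagged participants.

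**The case against.** The best reply is that the SAP is less open than it looks. Potential Hy's law has a first-dose start. End of Treatment is confined to the open-label period. By-visit windows begin at Treatment Day 1, so a Visit 1 held before the first-dose date has no by-visit row. Direct rollover is the default route, and those data can fairly be called lead-in data. The group that is clearly affected is one the plan says only may exist. All of this stands and is why the point is limited as it is. It does not supply a start for the PCS, Table 11-2 or QTcF-increase counts.

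A second reply is that the harm is small. Everyone who discontinues should have Visit 11/ET assessments, so entering a denominator on Visit 1 alone requires no post-dose sample from that visit or any other. Table 11-2 has no normal-baseline requirement, so its lowest rows already include people elevated before any treatment. The study is descriptive, and extra flags over-report. The lab PCS display shows every postbaseline value, and 18.3 puts all assessments in the listings. This stands as a limit on size. It does not help a reader of the summary tables, which would not separate Visit 1-only cases.

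A reader might also infer that a Week 4 ECG row would be almost wholly pre-dose. Protocol 8.4.1.2 schedules no Week 4 ECG, and table specifications are in a separate document, so nothing shows such a row will exist.

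**Conclusion.** The point holds and should be fixed. Under the SAP as written, a gap entrant's pre-dose Visit 1 values enter the lab, vital-sign and ECG PCS counts, Table 11-2 other than potential Hy's law, and the QTcF-increase table. For direct rollovers two programmers could reasonably produce different tables. The Week 4 effect covers labs and vital signs only and depends on the first dose being on the Visit 1 date. Visit 1 can serve as End of Treatment only when no later on-treatment value exists.

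The number affected cannot be derived. The documents give no per-visit abnormality rates, lead-in allocation or size of the gap group. The effect is probably small where the threshold lies far above a Visit 1 limit. It is least protected where Visit 1 has no numeric limit, such as alkaline phosphatase, or only an absolute one, as for QTcF change. In the lowest Table 11-2 categories, a participant dosed before a Visit 1 ALT above 1 × ULN is known stays in the Safety Population and is counted.

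A reader might infer a percentage inflation from Step 5. With an assumed equal and independent flag probability p at each ECG, the ratio of 1 − (1 − p)^4 to 1 − (1 − p)^3 gives about 32% to 33% more flagged participants for p of 0.2% to 2%. The documents do not support that figure. The p values are invented, Visit 1 ECGs are screened, and only some participants' Visit 1 values clearly enter. No inflation is claimed.

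**What to change.** In SAP 18.1 and 18.3, define postbaseline for the extension's lab, vital-sign and ECG summaries as assessed after the first open-label dose, with Visit 1 values treated as pre-dose for all three enrollment categories. Apply this to the numerators and denominators of the PCS, Table 11-2 and QTcF-increase tables in 11.2 to 11.4, and to End of Treatment. Start the Week 4 window at Treatment Day 2. Keep the lead-in baseline for change from baseline. In the same edit, state whether the Hy's law and post-treatment QTcF start points mean the open-label dose; that is a clarification only.

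This extends to these measures the open-label limit already given to TEAEs and End of Study. It costs SAP wording and one programming flag and needs no new data. The downside is slightly smaller denominators, because participants with no value after the first open-label dose drop out.

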18.4 MISSING DATE OF THE LAST DOSE OF STUDY TREATMENT

When the date of the last dose of open-label study treatment is missing, all efforts should be made to obtain the date from the Investigator. If it is still missing after all efforts have been made, the last available study medication date will be used in the calculation of treatment duration.

18.5 MISSING SEVERITY ASSESSMENT FOR ADVERSE EVENTS

If severity is missing for an AE that started before the date of the first dose of open-label study treatment, an intensity of mild will be assigned. If severity is missing for an AE that started on or after the date of the first dose of open-label study treatment, an intensity of severe will be assigned. The imputed values for severity assessment will be used for the incidence summary; the values will be shown as missing in the data listings.

18.6 MISSING CAUSAL RELATIONSHIP TO STUDY DRUG FOR ADVERSE EVENTS

If the causal relationship to the open-label study treatment is missing for an AE that started on or after the date of the first dose of open-label study treatment, a causality of yes will be assigned. The imputed values for causal relationship to open-label study treatment will be used for the incidence summary; the values will be shown as missing in the data listings.

18.7 MISSING DATE INFORMATION FOR ADVERSE EVENTS

The following imputation rules only apply to cases in which the start date for AEs is incomplete (ie, partly missing).

Missing month and day

- If the year of the incomplete start date is the same as the year of the first dose of open-label study treatment, the month and day of the first dose of open-label study treatment will be assigned to the missing fields

- If the year of the incomplete start date is before the year of the first dose of open-label study treatment, *December 31* will be assigned to the missing fields
- If the year of the incomplete start date is after the year of the first dose of open-label study treatment, *January 1* will be assigned to the missing fields

Missing month only

- If only the month is missing, the day will be treated as missing and both the month and the day will be replaced according to the above procedure

Missing day only

- If the month and year of the incomplete start date are the same as the month and year of the first dose of open-label study treatment, the day of the first dose of open-label study treatment will be assigned to the missing day
- If either the year of the incomplete start date is before the year of the date of the first dose of open-label study treatment or if both years are the same but the month of the incomplete start date is before the month of the date of the first dose of open-label study treatment, the last day of the month will be assigned to the missing day
- If either the year of the incomplete start date is after the year of the date of the first dose of open-label study treatment or if both years are the same but the month of the incomplete start date is after the month of the date of the first dose of open-label study treatment, the first day of the month will be assigned to the missing day

If the stop date is complete and the imputed start date as above is after the stop date, the start date will be imputed by the stop date.

If the start date is completely missing and the stop date is complete, the following algorithm will be used to impute the start date:

- If the stop date is after the date of the first dose of open-label study treatment, the date of the first dose of open-label study treatment will be assigned to the missing start date
- If the stop date is before the date of the first dose of open-label study treatment, the stop date will be assigned to the missing start date

18.8 MISSING DATE INFORMATION FOR PRIOR OR CONCOMITANT MEDICATIONS

For prior or concomitant medications, including rescue medications, incomplete (ie, partly missing) start dates and/or stop dates will be imputed. When the start date and the stop date are both incomplete for a participant, the start date will be imputed first.

18.8.1 Incomplete Start Date

The following rules will be applied to impute the missing numeric fields for an incomplete prior or concomitant medication start date. If the stop date is complete (or imputed) and the imputed start date is after the stop date, the start date will be imputed using the stop date.

Missing month and day

- If the year of the incomplete start date is the same as the year of the first dose of open-label study treatment, the month and day of the first dose of open-label study treatment will be assigned to the missing fields
- If the year of the incomplete start date is before the year of the first dose of open-label study treatment, *December 31* will be assigned to the missing fields
- If the year of the incomplete start date is after the year of the first dose of open-label study treatment, *January 1* will be assigned to the missing fields

Missing month only

- If only the month is missing, the day will be treated as missing and both the month and the day will be replaced according to the above procedure

Missing day only

- If the month and year of the incomplete start date are the same as the month and year of the first dose of open-label study treatment, the day of the first dose of open-label study treatment will be assigned to the missing day
- If either the year of the incomplete start date is before the year of the date of the first dose of open-label study treatment or if both years are the same but the month of the incomplete start date is before the month of the date of the first dose of open-label study treatment, the last day of the month will be assigned to the missing day.

- If either the year of the incomplete start date is after the year of the date of the first dose of open-label study treatment or if both years are the same but the month of the incomplete start date is after the month of the date of the first dose of open-label study treatment, the first day of the month will be assigned to the missing day

